16.2.1 Pregnancy Status

In the rare event that β -hCG is elevated as a tumor marker, pregnancy should be excluded. At minimum, this requires obstetrics evaluation, serial β -hCG measurements and ultrasound to exclude pregnancy.

16.3 Keyboard Design

Dose Escalation Rules

Dose escalation for schedule 1 and schedule 2 will follow the keyboard design. The table below in Section 16.3.1 provides the decision rules for the keyboard design when the target DLT rate is 30% (and the acceptable range is 25-33.3%). The columns in the table in Section 16.3.1 represent the number of evaluable subjects at the current dose level, the rows present the action to be taken and the numbers in the table itself are the number of DLTs. As an example, if 3 evaluable subjects have been treated at the current dose level, and 0 of those 3 subjects experience a DLT, then dose escalation can occur, and new subjects will be enrolled 1 dose level higher. If 1 of the 3 subjects experience a DLT, the dose stays the same and new subjects are enrolled at the same dose level. If 2 of the 3 subjects experience a DLT, de-escalation is required, and new subjects are enrolled 1 dose level lower.

See the specific rules for each schedule below for details on how the table in Section 16.3.1 is used. Scenarios have also been provided at the end of this appendix to help illustrate how the keyboard design and table are used in practice.

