9.2 Sample Size and Statistical Hypotheses

9.2.1 Dose Escalation

The planned sample size for the dose escalation part of the study is 63 subjects. For Schedule 1, the maximum planned sample size for dose escalation will be 42 subjects, and for Schedule 2, the

maximum planned sample size for dose escalation will be 15 subjects. The planned number of subjects to obtain additional pharmacodynamic data at select dose levels is approximately 6 subjects.

These sample sizes for dose escalation were chosen based on simulation results demonstrating good operating characteristics (see tables below) with these sample sizes using the Keyboard design (see dose escalation rules in Appendix Section 16.3). **NOTE:** The maximum planned sample sizes may be revised if additional DLs are evaluated or if more subjects (i.e., subjects available for dosing beyond the number required in a cohort) are enrolled than anticipated. The Sponsor, in consultation with the SMC, may also elect to add subjects if additional safety data are needed to select a dose and schedule for the expansion cohorts. Six (6) subjects must be treated at a dose level to confirm safety and tolerability before a dose can be used in an expansion cohort.

All simulation results are based on 5000 simulations and assume the following:

- The target DLT rate is 30% (acceptable range of 25-33.3%)
- Dose escalation will stop early if 12 subjects are enrolled at the same DL (See Scenarios 1 and 3 in Appendix Section 16.3)
- If there is more than a 95% chance that the current dose is above the MTD, that dose and higher doses will be eliminated from the trial to prevent exposing future subjects to overly toxic doses

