For Schedule 1, with a maximum of 42 subjects, the chance of selecting the true MTD is at least 40% for a range of possible scenarios. With single subject cohorts to start, followed by 3 subject cohorts, results will likely be somewhere in between the 2 sets of simulations provided, but should still provide at least 40% precision in selecting the MTD.

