16.3.1 Keyboard Design Decision Rules

Action	Number of evaluable subjects treated at the current dose level											
	1	2	3	4	5	6	7	8	9	10	11	12
Escalate if # of DLT ≤	0	0	0	0	1	1	1	1	2	2	2	2
Stay at same dose if # of DLT =	NA	NA	1	1	NA	2	2	2	3	3	3	3 or 4
De-escalate if # of DLT ≥	1	1	2	2	2	3	3	3	4	4	4	5
Eliminate if # of DLT ≥	NA	NA	3	3	4	4	5	5	5	6	6	7

NOTES:

- "Eliminate" means that the current and higher doses are eliminated from the trial to prevent treating any future subjects at these doses because they are overly toxic. When a dose is eliminated, automatically de-escalate the dose to the next lower level. If the lowest dose is eliminated, stop the trial for safety. In this case, no dose should be selected as the MTD.
- If the current dose is the lowest dose and the rule indicates dose de-escalation, treat new subjects at the lowest dose unless the number of DLTs reaches the elimination boundary, at which point terminate the trial for safety.
- If the current dose is the highest dose and the rule indicates dose escalation, treat new subjects at the highest dose.

16.3.1.1 Dose Escalation – Schedule 1

See Section 3.2.4 for the dose levels to be evaluated in schedule 1.

The first subject will be enrolled at Dose Level 1 in a single subject cohort. Single subject cohorts will be enrolled until:

- The subject in a single subject cohort experiences \geq Grade 2 toxicity (see Section 3.2.5) or a DLT **OR**
- Dose Level 6 is reached without evidence of a DLT or other \geq Grade 2 toxicity

If a subject in a single subject cohort experiences \geq Grade 2 toxicity or a DLT, 2 additional subjects will be added at that dose level (for a total of 3). Once a single subject cohort is expanded to 3, having a \geq Grade 2 toxicity no longer guides dose escalation (only DLTs do) and subsequent cohorts will now include at least 3 subjects. **NOTE:** If a subject in a single subject cohort is not evaluable, an additional single subject cohort should be enrolled at the same dose level. More than 1 subject may be enrolled in a cohort if additional subject(s) are available for dosing after consultation with the Sponsor.

Once cohorts of at least 3 subjects begin enrollment (after expansion of a single subject cohort to 3 or at Dose Level 6), the table in Section 16.3.1 will be used to guide dose escalation.

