#### 3.1 Study Design

The study design consists of Dose Escalation and Dose Expansion cohorts. The screening period will be 21 days prior to the first dose in the dose-escalation cohorts. Dosing will occur in cycles of 28 days until one of the following criteria applies: disease progression per iRECIST or RECIL 2017, death, intercurrent illness that prevents further administration of treatment, unacceptable AE(s), participant decides to withdraw from the study, general or specific changes in the participant's condition render the participant unacceptable for further treatment in the judgment of the investigator, participant non-compliance, pregnancy, termination of the study by Sponsor. Response and disease progression will be assessed at predetermined intervals.

Subjects with any of the following malignancies (including specific subtypes) may be enrolled in Dose Escalation: melanoma, NSCLC (squamous cell or adenocarcinoma or adeno-squamous), urothelial cancer, HNSCC, squamous cell cervical cancer, gastric or GEJ adenocarcinoma, SCCA, Skin-SCC, RCC, HL, MSI-H or MMRD solid tumors excluding CNS malignancies. The tumor types for dose expansion will be determined after review of data collected during dose escalation and will be selected from the dose escalation list of malignancies.

In the dose escalation phase of the study, subjects will be enrolled into sequential dose levels (DL) as outlined in Section 3.2 and Table 2. Enrollment into a DL cohort will follow the Keyboard Design with a target DLT rate of 30% (and the acceptable range is 25-33.3%), as in Table 1.

Two possible schedules (Schedule 1 and Schedule 2) may be explored. Schedule 1 will be evaluated first. A transition to Schedule 2 may be implemented for reasons outlined in Protocol Section 3.2.7. If Schedule 2 is opened, the Sponsor may also elect to stop enrollment in Schedule 2 early (e.g., based on safety) and resume enrollment in Schedule 1. The MTD or MAD may be determined for either schedule 1 or Schedule 2. Alternatively, a less intensive dosing schedule may be instituted if safety and pharmacodynamic data on Schedule 1 supports less frequent dosing of SL-279252.

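### Does the stated 25-33.3% range contradict the printed Keyboard decision table and the simulations built on it?

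*Protocol*

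**What the plan says.** Protocol 16.3 introduces the table in 16.3.1 as one that "provides the decision rules for the keyboard design when the target DLT rate is 30% (and the acceptable range is 25-33.3" per cent. Protocol 9.2.1 lists the same target and range among the simulation assumptions, and refers to the appendix for the escalation rules that were simulated. SAP 3.1 describes enrolment by "Keyboard Design with a target DLT rate of 30% (and the acceptable range is 25-33.3%), as in Table 1".

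The table prints an action for every count of DLTs at 1 to 12 evaluable subjects. The row "Stay at same dose if # of DLT" includes 1/3, 2/6, 3/9 and 4/12. The text repeats one of these in words: "If 1 of the 3 subjects experience a DLT, the dose stays the same and new subjects are enrolled at the same dose level". For overly toxic doses, 9.2.1 adds: "If there is more than a 95% chance that the current dose is above the MTD, that dose and higher doses will be eliminated". Protocol 9.2.1.1 concludes that "the chance of selecting the true MTD is at least 40% for a range of possible scenarios", and 9.2.1.2 says the same for Schedule 2.

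Neither document states a prior, a key width or layout, or a rule for choosing the action from the data. Elsewhere the range serves only to decide whether an MTD or a MAD is reported (Protocol 9.1 and 9.4.1.1).

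**The concern.** The range is the stated basis of the dose-decision table and a stated simulation input. Someone who tries to regenerate the table from the named design, the 30% target and a 25-33.3% target key, with the usual uniform prior, gets a different action at four cells. Two of them, 1/3 and 2/6, are common decision points in cohorts of 3, and the worked scenarios use them repeatedly.

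If the trial ran on that other rule, correct selection with cohorts of 3 would fall below the quoted 40% in several scenarios. One might then think that either the table or the quoted performance is wrong. Both serve the primary objective of finding the MTD.

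**Working it through.** **Inputs.** Target 0.30 and range 0.25 to 1/3 (Protocol 16.3, SAP 3.1). Printed table for n = 1 to 12 (Protocol 16.3.1, SAP Table 1). Elimination at more than 95% posterior probability of exceeding the target; stop at 12 subjects on one dose; 5,000 simulations (Protocol 9.2.1). Maximum sizes 42 and 15 (9.2.1.1, 9.2.1.2). *Assumed, because not stated:* prior Beta(1,1), keys of equal width (1/3 − 1/4 = 1/12), and an action set by the key with the largest posterior mass.

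**1. What the assumed rule reproduces.** It gives all 12 entries of the Escalate row. With y DLTs in n subjects, the posterior is Beta(1+y, 1+n−y). Applying Pr(rate > 0.30) > 0.95 gives the Eliminate row from n = 3 on (n = 1 and 2 are printed NA).

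**2. Where it differs.** At 1/3 the posterior is Beta(2,3), with distribution function F(x) = 6x² − 8x³ + 3x⁴.

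- F(1/4) = 0.26172, F(1/3) = 0.40741, F(5/12) = 0.55339
- target key: 0.40741 − 0.26172 = 0.14569
- next key up: 0.55339 − 0.40741 = 0.14598

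The upper key wins by 0.0003, so this rule de-escalates where the table says stay. The four cells that differ are:

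| DLTs/n | key 25-33.3% | key 33.3-41.7% | difference |
|---|---|---|---|
| 1/3 | 0.14569 | 0.14598 | 0.0003 |
| 2/6 | 0.18576 | 0.18649 | 0.0007 |
| 3/9 | 0.21661 | 0.21786 | 0.0013 |
| 4/12 | 0.24192 | 0.24376 | 0.0018 |

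In all four the observed proportion is exactly 1/3. Under a uniform prior the posterior mode is y/n, so it sits on the boundary between the two keys, and slight right skew tips the balance.

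**3. How far this depends on the assumption.** With a uniform prior and a 25% lower limit, upper limits from about 33.5% to 36.6% give the printed table exactly. With the key kept at 25% to 1/3, Beta(0.5,0.5) fails at three different cells (1/4, 2/8, 3/12), while Beta(1.02,1.11) fails at none.

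**4. The range read as inclusive limits on the observed proportion.** Escalate below 25%, stay from 25% to 33.3%, de-escalate above:

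| n | highest that escalates | stays | lowest that de-escalates |
|---|---|---|---|
| 1 | 0/1 | none | 1/1 |
| 2 | 0/2 | none | 1/2 = 50% |
| 3 | 0/3 | 1/3 = 33.3% | 2/3 |
| 4 | 0/4 | 1/4 = 25% | 2/4 |
| 5 | 1/5 = 20% | none | 2/5 = 40% |
| 6 | 1/6 | 2/6 = 33.3% | 3/6 |
| 7 | 1/7 | 2/7 = 28.6% | 3/7 |
| 8 | 1/8 | 2/8 = 25% | 3/8 = 37.5% |
| 9 | 2/9 = 22.2% | 3/9 = 33.3% | 4/9 |
| 10 | 2/10 | 3/10 = 30% | 4/10 |
| 11 | 2/11 | 3/11 = 27.3% | 4/11 = 36.4% |
| 12 | 2/12 | 3/12, 4/12 | 5/12 |

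Every entry equals the printed table, including NA for stay at n = 1, 2 and 5.

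**5. Which rule was simulated.** Running the printed table through the 22 published runs (12,000 trials each, isotonic selection) gives correct selection within 1.6 points of print and mean size within 0.2 subjects. The widest gap is Schedule 2 scenario 1, 66.0% against 64.36%. Its standard error is √(0.6436 × 0.3564 × (1/5,000 + 1/12,000)) = 0.81 points, so the gap is about two standard errors and the largest of 22. The uniform-prior 25-33.3% rule does not match. With cohorts of 3 it gives 32.3% in Schedule 1 scenario 9 (published 47.6%) and 32.6% in Schedule 2 scenario 4 (published 51.84%). The simulations therefore describe the printed table, as 9.2.1 says.

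**The case for a change.** The best case for a change is that the range is offered as the basis of the table, and that the standard reading of a Keyboard design does not deliver it. The uniform prior is a natural choice: it recovers the Escalate row and the Eliminate row from n = 3. Rounding does not explain the gap, since upper limits of 0.333, 1/3, 0.334 and 0.335 all leave the same four differences. The priors found to close it at 25-33.3% are unusual. The observed-proportion reading is written nowhere and is not a posterior-key rule. A sentence on derivation would be cheap.

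All of that stands as a remark on transparency. It does not show an error. The documents call 25-33.3% an acceptable or target range for the DLT rate and never describe it as a key, so the contradiction appears only after the reader supplies a prior and a key layout. The low selection figures belong to a rule that the protocol neither prints nor simulates. Nobody running or analysing the trial has to regenerate the table: it is printed in full twice, and the MTD is chosen by isotonic regression against 0.30 with stated tie rules, which does not use the keys.

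**Conclusion.** No change follows. The decision table (identical in protocol and SAP), the sentence on 1 of 3, the worked scenarios, the 22 simulation runs and the statements of at least 40% correct selection agree with one another. The stated range also fits the table exactly when read as inclusive limits on the observed proportion.

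What remains is an unstated derivation. Under one assumed prior and key layout it matters at four boundary cells, by key-mass differences of 0.0003 to 0.0018. A sentence naming the generating rule would alter no decision, boundary or published figure. Reissuing the cells would disturb an operating rule that is already consistent.

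The conclusion rests on the printed table being what the trial follows, which both documents direct. The simulation check also assumed small continuity constants and inverse-variance weights in the isotonic step, which the documents do not give; the printed-table runs matched with them. Nothing here says which action at those cells is clinically preferable.

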16.3.1 Keyboard Design Decision Rules

Action	Number of evaluable subjects treated at the current dose level											
	1	2	3	4	5	6	7	8	9	10	11	12
Escalate if # of DLT ≤	0	0	0	0	1	1	1	1	2	2	2	2
Stay at same dose if # of DLT =	NA	NA	1	1	NA	2	2	2	3	3	3	3 or 4
De-escalate if # of DLT ≥	1	1	2	2	2	3	3	3	4	4	4	5
Eliminate if # of DLT ≥	NA	NA	3	3	4	4	5	5	5	6	6	7

NOTES:

- "Eliminate" means that the current and higher doses are eliminated from the trial to prevent treating any future subjects at these doses because they are overly toxic. When a dose is eliminated, automatically de-escalate the dose to the next lower level. If the lowest dose is eliminated, stop the trial for safety. In this case, no dose should be selected as the MTD.
- If the current dose is the lowest dose and the rule indicates dose de-escalation, treat new subjects at the lowest dose unless the number of DLTs reaches the elimination boundary, at which point terminate the trial for safety.
- If the current dose is the highest dose and the rule indicates dose escalation, treat new subjects at the highest dose.

16.3.1.1 Dose Escalation – Schedule 1

See Section 3.2.4 for the dose levels to be evaluated in schedule 1.

The first subject will be enrolled at Dose Level 1 in a single subject cohort. Single subject cohorts will be enrolled until:

- The subject in a single subject cohort experiences \geq Grade 2 toxicity (see Section 3.2.5) or a DLT **OR**
- Dose Level 6 is reached without evidence of a DLT or other \geq Grade 2 toxicity

If a subject in a single subject cohort experiences \geq Grade 2 toxicity or a DLT, 2 additional subjects will be added at that dose level (for a total of 3). Once a single subject cohort is expanded to 3, having a \geq Grade 2 toxicity no longer guides dose escalation (only DLTs do) and subsequent cohorts will now include at least 3 subjects. **NOTE:** If a subject in a single subject cohort is not evaluable, an additional single subject cohort should be enrolled at the same dose level. More than 1 subject may be enrolled in a cohort if additional subject(s) are available for dosing after consultation with the Sponsor.

Once cohorts of at least 3 subjects begin enrollment (after expansion of a single subject cohort to 3 or at Dose Level 6), the table in Section 16.3.1 will be used to guide dose escalation.

- There will be a 3-day stagger between the first and second subjects enrolled at a given dose level. **NOTE:** This requirement may change based on emerging data as per the SMC.
- The column corresponding to the total number of evaluable subjects treated at the current dose level should be used to make the appropriate decision (i.e., escalate, stay at the same dose, de-escalate or eliminate).
- If a subject is not evaluable, a decision can still be made based on the total number of subjects who are evaluable at the current dose without enrolling an additional subject (unless all subjects in a cohort are not evaluable*).
- More than 3 subjects may be enrolled in a cohort if additional subject(s) are available for dosing after consultation with the Sponsor.

***NOTE:** If all subjects in a cohort are not evaluable, an additional cohort should be enrolled at the same dose level.

Dose escalation for schedule 1 may continue until:

- The trial is stopped for safety **OR**
- The maximum sample size of 42 subjects is reached **OR**
- The maximum sample size has not been reached but 12 subjects have been enrolled at the current dose level **OR**

- The Sponsor, in consultation with the SMC, decides to stop enrollment in schedule 1 early (e.g., based on safety, pharmacodynamics) and begin enrollment in schedule 2 (see Section 3.2.7)

NOTE: The maximum sample size of 42 may be revised if additional dose levels are evaluated or if more additional subjects (i.e., subjects available for dosing beyond the number required in a cohort) are enrolled than anticipated. The Sponsor, in consultation with the SMC, may also elect to add subjects if additional safety data are needed to select a dose and schedule for the expansion cohorts. Six (6) subjects must be treated at a dose level to confirm safety and tolerability before a dose can be used in an expansion cohort.

16.3.1.2 Dose Escalation – Schedule 2

See Section 3.2.4 for the dose levels to be evaluated if schedule 2 is opened.

Subjects will be enrolled in cohorts of 3, with the table in Section 16.3.1 used to guide dose escalation.

- There will be a 3-day stagger between the first and second subjects enrolled at a given dose level. **NOTE:** This requirement may change based on emerging data as per the SMC.
- The column corresponding to the total number of evaluable subjects treated at the current dose level should be used to make the appropriate decision (i.e., escalate, stay at the same dose, de-escalate or eliminate).
- If a subject is not evaluable, a decision can still be made based on the total number of subjects who are evaluable at the current dose without enrolling an additional subject (unless all subjects in a cohort are not evaluable*).

More than 3 subjects may be enrolled in a cohort if additional subject(s) are available for dosing after consultation with the Sponsor.

***NOTE:** If all subjects in a cohort are not evaluable, an additional cohort should be enrolled at the same dose level.

Dose escalation for schedule 2 may continue until:

[figure not shown]
- The trial is stopped for safety **OR**
- The maximum sample size of 15 subjects is reached **OR**
- The maximum sample size has not been reached but 12 subjects have been enrolled at the current dose level **OR**
- The Sponsor, in consultation with the SMC, decides to stop enrollment in schedule 2 early (based on safety.) and resume enrollment in schedule 1 or begin enrollment in dose expansion*

*At least 6 subjects will be enrolled at the dose level to be used during dose expansion and sufficient safety follow-up completed to confirm safety and tolerability (as determined by the SMC) before a decision can be made to begin dose expansion early.

NOTE: The maximum sample size of 15 may be revised if additional dose levels are evaluated or if more additional subjects (i.e., subjects available for dosing beyond the number required in a cohort) are enrolled than anticipated. The Sponsor, in consultation with the SMC, may also elect to add subjects if additional safety data are needed to select a dose and schedule for the expansion cohorts.

16.3.1.3 Keyboard Design Scenarios – Schedule 1

Scenario #1:

[figure not shown]

NOTE: All subjects in Scenario #1 are evaluable.

1. Subject #1 is enrolled at Dose Level 1 in a single subject cohort. Subject #1 does not experience a DLT or a \geq Grade 2 toxicity, so dose escalation is allowed and Subject #2 is enrolled at Dose Level 2 in a single subject cohort.
2. Subject #2 does not experience a DLT or a \geq Grade 2 toxicity, so dose escalation is allowed and Subject #3 is enrolled at Dose Level 3 in a single subject cohort.
3. Subject #3 experiences a \geq Grade 2 toxicity, so 2 additional subjects (Subjects #4 and #5) are enrolled at Dose Level 3. **NOTE:** Having a \geq Grade 2 toxicity no longer guides dose escalation (only DLTs do) and subsequent cohorts will now include at least 3 subjects.

4. Zero (0) of the 3 total subjects enrolled at Dose Level 3 experience a DLT, so following the table in Section 16.3.1, dose escalation is allowed and the next 3 subjects (Subjects #6, #7 and #8) are enrolled at Dose Level 4.
5. Zero (0) of the 3 subjects enrolled at Dose Level 4 experience a DLT, so following the table in Section 16.3.1, dose escalation is allowed and the next 3 subjects (Subjects #9, #10 and #11) are enrolled at Dose Level 5.
6. One (1) of the 3 subjects enrolled at Dose Level 5 experience a DLT, so following the table in Section 16.3.1, the next 3 subjects (Subjects #12, #13 and #14) are also enrolled at Dose Level 5.
7. Only 1 of the 6 total subjects enrolled at Dose Level 5 experience a DLT, so following the table in Section 16.3.1, dose escalation is allowed and the next 3 subjects (Subjects #15, #16 and #17) are enrolled at Dose Level 6.
8. Two (2) of the 3 subjects enrolled at Dose Level 6 experience a DLT, so following the table in Section 16.3.1, de-escalation is required and the next 3 subjects (Subjects #18, #19 and #20) are enrolled at Dose Level 5.
9. Two (2) of the 9 total subjects enrolled at Dose Level 5 experience a DLT, so following the table in Section 16.3.1, dose escalation is allowed and the next 3 subjects (Subjects #21, #22 and #23) are enrolled at Dose Level 6.
10. Three (3) of the 6 total subjects enrolled at Dose Level 6 experience a DLT, so following the table in Section 16.3.1, de-escalation is required and the next 3 subjects (Subjects #24, #25 and #26) are enrolled at Dose Level 5.
11. The maximum sample size of 42 subjects has not been reached, but 12 subjects have now been enrolled at Dose Level 5, so dose escalation can stop early and the MTD can be determined based on the 26 subjects enrolled.

Scenario #2:

[figure not shown]

NOTE: All subjects in Scenario #2 are evaluable.

1. Subject #1 is enrolled at Dose Level 1 in a single subject cohort. Subject #1 does not experience a DLT or a \geq Grade 2 toxicity, so dose escalation is allowed and Subject #2 is enrolled at Dose Level 2 in a single subject cohort.
2. Subject #2 does not experience a DLT or a \geq Grade 2 toxicity, so dose escalation is allowed and Subject #3 is enrolled at Dose Level 3 in a single subject cohort.
3. Subject #3 does not experience a DLT or a \geq Grade 2 toxicity, so dose escalation is allowed and Subject #4 is enrolled at Dose Level 4 in a single subject cohort.
4. Subject #4 experiences a \geq Grade 2 toxicity, so 2 additional subjects (Subjects #5 and #6) are enrolled at Dose Level 4. **NOTE:** Having a \geq Grade 2 toxicity no longer guides dose escalation (only DLTs do) and subsequent cohorts will now include at least 3 subjects.
5. One (1) of the 3 total subjects enrolled at Dose Level 4 experience a DLT (**NOTE:** the \geq Grade 2 toxicity is not used for the dose escalation decision), so following the table in Section 16.3.1, the next 3 subjects (Subjects #7, #8 and #9) are also enrolled at Dose Level 4.

6. Only 1 of the 6 total subjects enrolled at Dose Level 4 experience a DLT, so following the table in Section 16.3.1, dose escalation is allowed and the next 3 subjects (Subjects #10, #11 and #12) are enrolled in Dose Level 5.
7. One (1) of the 3 subjects enrolled at Dose Level 5 experience a DLT, so following the table in Section 16.3.1, the next 3 subjects (Subjects #13, #14 and #15) are also enrolled at Dose Level 5.
8. Only 1 of the 6 total subjects enrolled at Dose Level 5 experience a DLT, so following the table in Section 16.3.1, dose escalation is allowed and the next 3 subjects (Subjects #16, #17 and #18) are enrolled at Dose Level 6.
9. Zero (0) of the 3 subjects enrolled at Dose Level 6 experience a DLT, so following the table in Section 16.3.1, dose escalation is allowed and the next 3 subjects (Subjects #19, #20 and #21) are enrolled at Dose Level 7.
10. One (1) of the 3 subjects enrolled at Dose Level 7 experience a DLT, so following the table in Section 16.3.1, the next 3 subjects (Subjects #22, #23 and #24) are also enrolled at Dose Level 7.
11. Two (2) of the 6 total subjects enrolled at Dose Level 7 experience a DLT, so following the table in Section 16.3.1, the next 3 subjects (Subjects #25, #26 and #27) are also enrolled at Dose Level 7.
12. Only 2 of the 9 total subjects enrolled at Dose Level 7 experience a DLT, so following the table in Section 16.3.1, dose escalation is allowed and the next 3 subjects (Subjects #28, #29 and #30) are enrolled at Dose Level 8.
